6.6.1.5.1 Severe Immune-Mediated Skin Adverse Events

When a patient is treated with camidanlumab tesirine in combination with pembrolizumab, and there are cases of severe immune-mediated skin adverse events related to camidanlumab tesirine, the following recommendations for camidanlumab tesirine should be followed. These recommendations align with current guidances provided in the pembrolizumab prescribing information:

- Grade 3 immune-mediated skin AE, drug reaction with eosinophilia and systemic symptoms (DRESS), suspected Stevens-Johnson syndrome (SJS), suspected toxic epidermal necrolysis (TEN): withhold treatment regimen
- Grade 4 immune-mediated skin AE, DRESS, confirmed SJS, confirmed TEN: treatment regimen permanently discontinued

6.6.1.6 Principles of Camidanlumab Tesirine Rechallenge

Exercise caution when considering resumption of camidanlumab tesirine after significant immune-related adverse events (irAEs) (\geq Grade 2). Close follow-up should be performed when resuming camidanlumab tesirine to monitor recurrent symptoms:

- If re-challenged and toxicity returns, permanently discontinue camidanlumab tesirine
- Assess patient's tumor status prior to rechallenge. If an objective response (complete or partial) to camidanlumab tesirine was achieved, resumption of camidanlumab tesirine may not be advisable due to risk of toxicity recurrence. Risks/benefits of restarting camidanlumab tesirine is to be discussed with Sponsor.

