6.6.1 Dose Delays and Modifications for Camidanlumab Tesirine

The Investigator may suspend camidanlumab tesirine dosing for up to 21 days for any patient who experiences any toxicity of any grade.

Resumption of dosing with camidanlumab tesirine after any suspension, even when longer than 21 days, is at the discretion of the Investigator on assessment of the patient's clinical condition and whether or not the patient is deriving potential clinical benefit from treatment with camidanlumab tesirine.

Guidelines for management of toxicities, when considered to be at least possibly related to camidanlumab tesirine, are detailed:

- in Section 6.6.1.1 for general toxicities (i.e., not specified in the below sections),
- in Section 6.6.1.2 for specific non-hematologic toxicities,
- in Section 6.6.1.3 for specific hematologic toxicities,

- in Section [6.6.1.4](#) for specific neurologic toxicities,
- in Section [6.6.1.5](#) for specific skin toxicities.

When a patient is treated with the combination of camidanlumab tesirine and pembrolizumab, the management of irAEs related to camidanlumab tesirine will follow the recommendations for the management of irAEs related to pembrolizumab in [Table 14 \(Appendix 13.4\)](#).

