6.6.1.1 Camidanlumab Tesirine Dose Modification Guidelines: General Toxicities

AE Grade	Camidanlumab Tesirine Management Guideline
1/2	No dose adjustment is required.
3/4	
First Occurrence:
 
Hold camidanlumab tesirine until improvement to \leqGrade 1 or Baseline.
 
If improvement to \leqGrade 1 or Baseline occurs prior to the next scheduled dose, continue camidanlumab tesirine at the original assigned dose level in subsequent treatment cycles.
 
If improvement to \leqGrade 1 or Baseline occurs >21 days from the last scheduled (but missed) camidanlumab tesirine dose, continue camidanlumab tesirine and reduce by 1 dose level from the original assigned dose in subsequent treatment cycles.
 
Second Occurrence:
 
Hold camidanlumab tesirine until improvement to \leqGrade 1 or Baseline.
 
If improvement to \leqGrade 1 or Baseline occurs prior to the next scheduled dose, reduce by 1 dose level from the original assigned dose in subsequent treatment cycles.
 
If improvement to \leqGrade 1 or Baseline occurs >21 days from the last scheduled (but missed) camidanlumab tesirine dose, continue camidanlumab tesirine and reduce by 2 dose levels from the original assigned dose in subsequent treatment cycles.
 
Otherwise, camidanlumab tesirine should be permanently discontinued.
 
Third Occurrence:
 
Permanently discontinue camidanlumab tesirine.

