Hy's law (AST and/or ALT $> 3 \times$ ULN and bilirubin $> 2 \times$ ULN)	-	
Permanently discontinue camidanlumab tesirine.
 
Hy's law defined as: AST and/or ALT $>3 \times$ ULN and bilirubin $>2 \times$ ULN, and without initial findings of cholestasis (ALP activity $<2 \times$ ULN) and no other reason that could explain the combination of increased transaminases and serum total bilirubin, such as viral hepatitis A, B, or C, preexisting or acute liver disease, or another drug capable of causing the observed injury.

Autoimmune toxicities (e.g., hypothyroidism, hyperthyroidism, hepatitis, other endocrinopathies)	≥ 1	
Need to be followed at least weekly to quickly detect deterioration and modify dosing as per general recommendations in Section 6.6.1.1 (can be done by telephone unless symptoms worsen).
 
Consider using American Society of Clinical Oncology (ASCO) guidelines for management of immune mediated toxicities (Brahmer, 2018, or local guidelines).
 
Specific guidelines for management of hyperthyroidism, hypothyroidism, and hepatitis are provided in the Appendix 13.5.

Selected Types of Infection: HSV1, HSV2, VZV, EBV, CMV, measles, Influenza A, Zika virus, Chikungunya virus, mycoplasma pneumonia, Campylobacter jejuni, enterovirus D68, or SARS-CoV-2.	Any Grade	
No dose adjustment is required; however, hold camidanlumab tesirine. Re-dosing must be delayed so that there is at least a 4-week window between symptom resolution and the next dose of camidanlumab tesirine.
 
If there is suspicion that a patient may have contracted the coronavirus disease COVID-19 (e.g., recent contacts with persons who tested positive and/or recent symptoms of respiratory tract infection and/or recent loss of smell and/or taste), a pathogen-directed SARS-CoV-2 test, such as PCR, should be performed. If the patient tests positive, a repeat test should be conducted 7 to 14 days later. If the patient repeatedly tests positive without having developed symptoms, dosing may proceed at the discretion of the Investigator.

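### When a monotherapy patient's related Grade 3/4 autoimmune toxicity recurs at Grade 3/4 on re-dosing, two recovery-time branches of Protocol 6.6.1.1 allow a reduced dose where 6.6.1.6 requires permanent discontinuation

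*Protocol*

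**What the plan says.** Four parts of Protocol Section 6.6.1 bear on this.

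- **6.6.1.6 (rechallenge).** For immune-related events of Grade 2 or higher: "If re-challenged and toxicity returns, permanently discontinue camidanlumab tesirine". The rule makes no exception for recovery time, dose level or higher grade. It is not confined to combination patients, whereas 6.6.1.5.1, just before it, is.
- **6.6.1.2 (autoimmune row, Grade 1 and above).** The instruction is to follow the patient at least weekly and "modify dosing as per general recommendations in Section 6.6.1.1". For three conditions the row adds: "Specific guidelines for management of hyperthyroidism, hypothyroidism, and hepatitis are provided in the Appendix 13.5".
- **6.6.1.1 (general ladder, Grade 3/4).** At the second occurrence the drug is held. If improvement "occurs prior to the next scheduled dose, reduce by 1 dose level from the original assigned dose in subsequent treatment cycles", the patient resumes at that lower dose. If improvement comes more than 21 days after the missed dose, the instruction is to continue and "reduce by 2 dose levels from the original assigned dose in subsequent treatment cycles". In any other case the drug is stopped. A third occurrence stops it unconditionally.
- **6.6.1 (opening text).** The tables apply to toxicities at least possibly related to camidanlumab tesirine. Also, "Resumption of dosing with camidanlumab tesirine after any suspension, even when longer than 21 days, is at the discretion of the Investigator". For combination patients, "the management of irAEs related to camidanlumab tesirine will follow the recommendations for the management of irAEs related to pembrolizumab in" Table 14 (Appendix 13.4).

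**The concern.** A site that meets a recurrent autoimmune event will naturally look it up in the autoimmune row, which leads to a ladder offering a reduced dose at the second occurrence. Section 6.6.1.6 says the same patient must stop. Nothing in the supplied text says which rule prevails, and nothing separates rechallenge from the resumption described in 6.6.1.1; 6.6.1.6 itself uses the two words interchangeably.

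The first thing at stake is patient safety. Immune-related events are among the important identified risks in Protocol 1.3, and a re-dosed patient is one whom another section of the same protocol would have withdrawn. The second is classification. SAP 4.3 counts as an important deviation a patient who met a mandatory discontinuation criterion but was kept on drug. Until precedence is stated, two people could classify the same re-dosed patient differently, and the patient would appear in the descriptive tables as a dose reduction and not as a discontinuation.

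**Working it through.** The plan has no figure to reproduce. The check traces one patient through both rules and then sizes the difference in dose.

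**Patient.** Monotherapy; related Grade 3 colitis; drug held; recovery; re-dosed; colitis returns at Grade 3; drug held; second recovery. Colitis is a suitable example: Protocol 8.1.1 lists it as autoimmune-mediated, it has no stop rule of its own in 6.6.1.2 to 6.6.1.5, and it is not among the three conditions sent to Appendix 13.5.

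**Action at the second Grade 3/4 occurrence**

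| Timing of second recovery | 6.6.1.2 row via 6.6.1.1 | 6.6.1.6 | Conflict? |
|---|---|---|---|
| Before the next scheduled dose | Resume, 1 level below original | Stop permanently | Yes |
| After the scheduled dose, but not more than 21 days past the missed dose | Stop (residual branch) | Stop permanently | No |
| More than 21 days past the missed dose | Continue, 2 levels below original | Stop permanently | Yes |

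The middle row is the literal reading of the residual branch in 6.6.1.1.

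**Outside the point**
- Combination patients (sent to Table 14).
- Thyroid events and hepatitis (Appendix 13.5).
- Events with their own stop rule, such as Hy's law cases (6.6.1.2), and GBS/polyradiculopathy and Grade 3 or higher peripheral neuropathy (6.6.1.4).
- Recurrences below Grade 3.

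**Size of the dose difference.** Protocol 1.3.4 reports 8 tested levels from 20 to 150 µg/kg. I assume these are Levels 1 to 8 of Table 4: 20, 30, 45, 60, 80, 100, 125, 150. Fraction retained = reduced level ÷ assigned level.

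- One level down: 20/30 = 67%, 30/45 = 67%, 45/60 = 75%, 60/80 = 75%, 80/100 = 80%, 100/125 = 80%, 125/150 = 83%. This is available from 7 of the 8 levels.
- Two levels down: 20/45 = 44%, 30/60 = 50%, 45/80 = 56%, 60/100 = 60%, 80/125 = 64%, 100/150 = 67%. This is available from 6 of the 8 levels.
- Only if the conditional Dose Level -1 (10 µg/kg, Protocol 6.3) is used: 10/20 = 50% one level down from 20, and 10/30 = 33% two levels down from 30.
- Under 6.6.1.6: 0%.

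**Patients.** Protocol 1.3.4 gives Grade 3 autoimmune events in 6.8% of 44 monotherapy patients (3/44 = 6.8%), regardless of relationship. The scenario also needs relatedness, recovery, re-dosing, Grade 3/4 recurrence and a second recovery in a conflicting branch. None of these is reported, so no rate or interval for affected patients can be derived.

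**The case against.** The best defence is that the texts can be followed together. The tables are guidelines, resumption is left to the Investigator, and 6.6.1 describes its ladder as "in Section 6.6.1.1 for general toxicities (i.e., not specified in the below sections". A permissive general ladder beside a specific stop rule reads naturally as specific over general, and a site that stops the drug complies with both. Part of this stands: the ladder allows re-dosing and does not compel it, so a reader should not infer that sites are ordered to re-dose. But discretion to resume does not turn an instruction to discontinue permanently into an option. The autoimmune row is also a specific rule, and it imports the ladder by name.

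Several stronger inferences are tempting and not supported.

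- *Every second recovery produces a conflict.* It does not: the residual branch of 6.6.1.1 stops the drug, as 6.6.1.6 does.
- *Leaving 6.6.1.6 out of the list in 6.6.1 shows that it is subordinate.* That list is organised by toxicity class, and rechallenge is not a class. The omission is weak evidence.
- *Three of 44 patients are affected.* That figure counts Grade 3 autoimmune events regardless of cause, not rechallenged recurrences.
- *The MTD is in doubt.* The monotherapy DLT window is the 21 days after first dosing (4.1.1, 6.5). On the planned three-weekly schedule, a recurrence after re-dosing falls later.

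The unseen appendices are a fair objection to certainty. The title of Table 14 covers events related to camidanlumab tesirine, and that table or Appendix 13.5 might settle the matter.

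Unnoticed re-dosing is also unlikely. Autoimmune-mediated events are AESIs (8.1.1), reported within 24 hours if serious, including recurrent episodes, and within 48 hours if not (8.2). Section 6.6.1.6 also calls for discussion of a restart with the Sponsor, although that sentence sits in the bullet on objective responders, and 1.3.4 lists no CR or PR in this arm.

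**Conclusion.** The conflict holds in the supplied text, in two of the three second-occurrence branches: recovery before the next scheduled dose, and recovery more than 21 days past the missed dose. It concerns monotherapy patients with a related autoimmune toxicity that is Grade 3/4 on both occasions and has neither its own stop rule nor Appendix 13.5 guidance. Where it applies, later cycles are given at 67 to 83% (one level down) or 44 to 67% (two levels down) of the assigned dose, without Dose Level -1, against none under 6.6.1.6.

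Severity is minor. Monotherapy enrolment was complete by 14 April 2021 (1.3.4), and treatment beyond one year needs case-by-case Sponsor review (4.2.2), so the practical reach is small and the number of affected patients may be zero. The SAP performs no hypothesis test that this could alter. Confidence is medium: the conclusion rests on Appendices 13.4 and 13.5 not settling precedence, which could not be checked.

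**What to change.** Add one sentence to the autoimmune row of Protocol 6.6.1.2: recurrence of an immune-related event after rechallenge is governed by 6.6.1.6 (permanent discontinuation) and not by the second-occurrence step of 6.6.1.1. Add a cross-reference to 6.6.1.6 in 6.6.1. Before issuing it, check that Appendices 13.4 and 13.5 agree.

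This adopts the stricter of two rules already in the protocol. It needs no new data, visits or SAP change, because SAP 4.3 already captures failure to withdraw drug once 6.6.1.6 is confirmed as governing. It can wait for the next amendment. The clinical cost is that a few patients who might have continued at a reduced dose would stop.

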6.6.2 Dose Delays and Modifications for Pembrolizumab

6.6.2.1 General rules

Dose reduction or dose-escalation are not permitted.

Management of immune-related AEs in patients treated with immune checkpoint inhibitor therapy, based on international guidelines (Brahmer, 2018; Haanen, 2017; Puzanov, 2017; NCCN, 2019) are shown in [Appendix 13.4](#).

Guidelines for management of toxicities, when considered to be at least possibly related to pembrolizumab, are detailed in [Appendix 13.4](#).

In the event of toxicity not relieved with optimal medical support, modifications in pembrolizumab administration include dose interruptions, delays in the start of the next cycle, and/or treatment discontinuation (refer to Section 6.6.2.2 and [Appendix 13.4](#)).

In the event of a delay in initiation of a planned Cycle of Study treatment for >21 days, the Sponsor should be contacted to discuss continuing the patient on pembrolizumab.

Pembrolizumab will be given at full dose when resumed after being held for toxicity.

If pembrolizumab is held because of AEs >12 weeks beyond the last dose, then the patient will be discontinued from pembrolizumab and will be followed for safety.

If pembrolizumab is discontinued due to significant irAE, camidanlumab tesirine could be continued, at lower dose level, after discussion with the Sponsor.

Investigators should inform Sponsor in case of immune-related AEs of any grade.

6.6.2.2 Holding Recommendations

If a patient experiences any Grade ≥ 3 toxicity, pembrolizumab must be held until the toxicity resolves to Grade 1 or less (Grade 1 or baseline for peripheral neuropathy).

For the dose recommendations per prescribing information, please refer to [Appendix 13.4](#).

6.6.2.3 Principles of Pembrolizumab Rechallenge

Exercise caution when considering resumption of pembrolizumab after significant irAEs. Close follow-up should be performed when resuming pembrolizumab to monitor recurrent symptoms:

- If re-challenged and toxicity returns, permanently discontinue pembrolizumab
- Assess patient's tumor status prior to rechallenge. If an objective response (complete or partial) to pembrolizumab was achieved, resumption of pembrolizumab may not be advisable due to risk of toxicity recurrence. Risks/benefits of restarting pembrolizumab is to be discussed with Sponsor.

With some exceptions (see [Appendix 13.4](#)), resumption of pembrolizumab following Grade 2 irAEs can be considered upon resolution to \leq Grade 1.

Consult with organ-specific specialists prior to resumption of immunotherapy as appropriate following an immunotherapy hold due to irAEs. For organ-specific considerations for pembrolizumab rechallenge after a hold, refer to [Appendix 13.4](#).

6.7 Overdose Management

For camidanlumab tesirine, the overdose is any dose given to a patient that exceeds the planned dose by 15% or more.

For pembrolizumab, an overdose is defined as any dose exceeding 5 times the prescribed dose for pembrolizumab (i.e., ≥ 1000 mg). No specific information is available on the treatment of overdose of pembrolizumab.

Any overdose, with or without associated AEs, drug should be held, and event must be promptly (i.e., within 24 hours after the time site personnel first learn about the event) reported to the Sponsor; in case of study treatment related AE, please refer to the dose delay and modification recommendation, listed in Section [6.6](#).

There are no data available to determine what the effects of overdose are and whether they can be reversed. Symptomatic treatment and standard supportive care measures for the management of any observed toxicity should be applied.

If feasible, a sample for PK analysis should be taken as close as possible to the overdose event.

6.8 Treatment Compliance

Administration of the study drug will be performed by the Investigator or a qualified designee; therefore, compliance will be verified by the study drug administration information.

6.9 Premedication and Supportive Care

6.9.1 Premedication for Camidanlumab Tesirine

Unless contraindicated, administer dexamethasone 4 mg orally BID, or equivalent, the day before camidanlumab tesirine administration (if possible), the day of camidanlumab tesirine administration (give at least 2 hours prior to administration when not given the day before; otherwise any time prior to administration), and the day after camidanlumab tesirine administration.

Patients who experience an infusion-related hypersensitivity reaction will receive the alternative premedication regimen specified in Section [6.9.4](#).

6.9.2 Premedication for Pembrolizumab

No premedication is required for pembrolizumab.

6.9.3 Treatment of Edema and Pleural Effusion

Spironolactone at standard doses should be administered for patients with weight gain greater than 1 kg from C1D1, new or worsening edema, and/or new or worsening pleural effusion. The dose of spironolactone may be titrated as clinically indicated. Additional diuretic support may be added if there is further increase in weight, edema, or pleural effusion. Additionally, patients should be advised to monitor their weight on a daily basis, at around the same time (preferably in the morning), and to notify the study site if they gain >1 kg (2.2 pounds) over Baseline.

6.9.4 Treatment and Prophylaxis of Infusion-Related Hypersensitivity Reactions

Medications for the treatment of severe hypersensitivity reactions, including anaphylaxis, should be available for immediate use and may be administered according to site standard treatment protocols.

Any patient who experiences an infusion-related hypersensitivity reaction should receive prophylactic treatment in subsequent cycles according to the guidelines below or per institutional SoC:

- On Day 1 of each cycle, patients will be instructed to take dexamethasone 20 mg orally 12 and 6 hours before the start of the camidanlumab tesirine infusion. When necessary, 12 and 6 hours before the first infusion may be defined as “immediately before sleeping” and “immediately after waking up.”
- On Day 1 of each cycle, patients will be given diphenhydramine hydrochloride 50 mg IV 30 minutes before the start of the camidanlumab tesirine infusion.
- On Day 1 of each cycle, patients will be given ranitidine (or equivalent) 50 mg IV 30 minutes before the start of the camidanlumab tesirine infusion.
- For 2 days following administration of camidanlumab tesirine on Day 1, patients are to take dexamethasone 4 mg orally BID.

6.9.5 Consideration for Skin Toxicity

6.9.5.1 Camidanlumab Tesirine

Skin toxicity has been reported in patients receiving camidanlumab tesirine for hematologic malignancies. Often, the toxicities manifested as rash were reported in sun exposed areas; it is therefore, recommended that precautions are taken to avoid exposure of skin to sunlight, even through glass (for example, use of sun protective clothing and sunglasses, sunscreen with a sun protection factor ≥ 30 applied every 2 hours, avoidance of being outside with no protection). Also, fragrance-free detergents and soaps are recommended.

Consideration should be given to corticosteroid therapy in patients who develop clinically significant skin toxicity (guidelines for dose modification in Section [6.6.1.5](#)).

Photographs of skin toxicity may be taken for documentation purposes at the discretion of the Investigator provided the patient has given consent for this specific assessment.

6.9.5.2 Pembrolizumab

Immune-related severe skin reactions have been reported in patients receiving pembrolizumab. Patients should be monitored for suspected severe skin reactions and other causes should be excluded. Based on the severity of the adverse reaction, pembrolizumab should be withheld or permanently discontinued, and corticosteroids should be administered (see [Appendix 13.4](#)).

Cases of Stevens-Johnson syndrome (SJS) and toxic epidermal necrolysis (TEN) have been reported in patients receiving pembrolizumab. For signs or symptoms of SJS or TEN, pembrolizumab should be withheld and the patient should be referred to a specialised unit for assessment and treatment. If SJS or TEN is confirmed, pembrolizumab should be permanently discontinued (see [Appendix 13.4](#)).

Caution should be used when considering the use of pembrolizumab in a patient who has previously experienced a severe or life-threatening skin adverse reaction on prior treatment with other immunestimulatory anticancer agents.

6.9.6 Diagnostic, Work-up, and Management of Polyradiculopathy/ Guillain-Barré Syndrome

It is strongly recommended starting management of polyradiculopathy/GBS with either intravenous immunoglobulin (IVIg) 0.4 g/kg/day for 5 days or plasma exchange (PLEX) once diagnosis of polyradiculopathy/GBS has been considered by a neurologist; this would be at CTCAE Grade 2 symptoms for neuropathy or Score 1 as per GBS disability scale ([Appendix 13.3](#)). It has to be considered that manifestation of polyneuropathy can be variable.

Diagnostic workup should include:

- Neurology consultation
- MRI spine with and without contrast to rule out compressive lesion and evaluate for nerve root enhancement or thickening
- Electrodiagnostic studies (nerve conduction studies)
- Serologic test for SARS-CoV-2 ([Alberti, 2020](#); [Toscano, 2020](#); [Zhao, 2020](#))
- Pulmonary function tests
- Lumbar puncture: CSF typically has albuminocytologic dissociation, i.e., protein elevation disproportionate to white blood cells (WBCs—although note that CSF WBCs are often elevated in GBS associated with immune checkpoint inhibitors)
- Serum antibody testing for GBS (ganglioside antibodies) when possible

Management includes:

- IVIg or PLEX as above
- If IVIg and/or PLEX do not result in improvement, consider using steroids ([Gu, 2017](#))
- Admission to inpatient unit with capability for rapid transfer to intensive care unit-level monitoring
- Frequent focused neurological examination (at least twice daily)
- Frequent pulmonary function monitoring
- Monitoring for autonomic dysfunction
- Non-opioid management of neuropathic pain
- Treatment of constipation/ileus
- Anticoagulation
- Physical therapy

